## Timeline

Table 3 Timeline for Proposed Study

Activity	Year Months	Year 1		Year 2		Year 3		Year 4	
		1-4	5-12	1-6	7-12	1-6	7-12	1-8	9-12
Hire/ train personnel									
Database refinement									
Data entry									
Subject enrollment									
Data collection									
Data management									
Analysis of final results									
Final results manuscripts and final grant report									

## **XII. DATA AND SAFETY MONITORING**

A Data and Safety Monitoring Plan (DSMP) will be implemented for the purpose of monitoring safety of the study, including but not limited to review of adverse events. Monthly DSMP meetings will include the PI, project director, biostatistician, data manager, and GRAs. The DSMP meetings will include review of all safety and adverse events data. Summary reports of data will be prepared by the data manager and project director. DSMP reports will consist of protocol compliance with inclusion/exclusion criteria, gender and minority and adverse events review. Written minutes of DSMB meetings with summaries of adverse events will be forwarded to the IRB and NIH as part of the annual reporting process. Research staff will report any adverse event immediately to the PI. Enrollment, study fidelity, and safety data will be reviewed regularly at study team monthly meetings. All adverse events will be reported to the TGH and USF IRBs, and the NIH, following institutional and NIH guidelines. We believe that the protocol is low risk and that this should be adequate.

## **XIII. MULTI-CENTER STUDIES**

N/A

## **XIV. INVOLVEMENT OF NON-USF INSTITUTIONS/SITES (DOMESTIC AND FOREIGN)**

N/A

## **XV. INVOLVEMENT OF INDEPENDENT INVESTIGATORS**

N/A

## **XVI. HUMAN SUBJECTS INSTRUCTIONS**

### **A. DESCRIPTION**

The proposed project will determine the optimal frequency of a tooth brushing intervention, by comparing three groups (once, twice, or three times daily), with the intent of informing the standard of nursing care for mechanically ventilated adults. As such, we believe this project meets the definition of "Human Subjects Research which involves an NIH-Defined Phase III Clinical Trial." Following obtainment of informed consent from the subject or LAR, subjects will be randomly assigned within 36 hours of intubation to one of three intervention groups which differ in frequency of tooth brushing (once, twice, or three times daily). The intervention, a standardized tooth brushing protocol developed and tested in the previous project, will be delivered by study personnel for 7 days, or until the subject is extubated if extubation occurs within the first 7 days. Data will be collected on study admission and every intervention day. For subjects who are extubated within the 7 day intervention period, data will also be collected on day 1,3, and 5 following extubation.

### **B. SUBJECT POPULATION**

Subjects will be recruited at Tampa General Hospital (TGH). TGH is a private not-for-profit hospital and one of the most comprehensive medical facilities in West Central Florida serving a dozen counties with a population in excess of 4 million. We will enroll 345 critically ill, mechanically ventilated subjects, ages 18 and older. We anticipate that the subjects will be representative of the population, as described in Table 4.

Table 4. Characteristics of Study Population, Geographic Area and Hospital (2010 estimated data)

Characteristics	Hillsborough County, FL	Hospital (inpatient)
Gender		
Male	49.3%	43.9%
Female	50.7%	56.1%
Ethnic category		
Hispanic or Latino	23.4%	
Not Hispanic or Latino	76.6%	
Racial category		
American Indian/Alaska Native	0.4%	0.2%
Asian	3.0%	0.6%
Native Hawaiian/Pac Islander	0%	0%
Black / African American	16.0%	20.7%
White	71.2%	73.6%
More than 2/ Other / Unknown	9.3%	5.0%
Average age	37.1	48.8

### **Inclusion of Women, Minorities and Children**

Inclusion of Women. TGH is a diverse clinical setting. Based on the patient characteristics of the study units in our current study, females make up approximately 40% of the population of each unit (about 10% less than the proportion of women in Hillsborough County, FL, or the entire TGH hospital population). We expect that recruitment of females will mirror these demographics. Our experiences during previous critical care studies show that recruitment of females is similar to that in the admission population. Therefore, it is anticipated that the subjects selected for this study will be representative in gender of the population of patients in the TGH ICUs. However, [name] and the Project Director will pay special attention to the admission of women to the unit. All women meeting inclusion criteria will be recruited. We will review the enrollment of women at our monthly study team meetings to ensure that we are meeting our target enrollment. Should we find that we are not meeting targets, we will immediately examine our enrollment data to determine if we have a recruitment issue or a temporary flux in unit admission of women. If it is a recruitment issue, we will analyze the enrollment data and discuss possible causes in order to determine a solution.

Inclusion of Minorities. TGH is also an ethnically and racially diverse clinical setting. Based on admission characteristics of the study units (Table 6: STICU and MRICU) minorities make up approximately 36% of the population of each unit. We expect that recruitment of minorities will also mirror these demographics. Our experiences during previous critical care studies show that recruitment of minorities is similar to that in the admission population. It is anticipated that the subjects selected for this study will be representative in ethnic background and race of the population of patients in the TGH ICUs. We intend to recruit minorities consistent with our accessible population. [name] and the Project Director will pay special attention to the admission of ethnic minorities to the units. All patients meeting inclusion criteria will be recruited. We will review the enrollment of racial and ethnic minorities at our monthly study team meetings to ensure that we are meeting our target enrollment. Should we find that we are not meeting targets, we will immediately examine our inclusion criteria in relation to the characteristics of subjects in the unit to determine if we have a recruitment issue or a temporary flux in minority admissions. If it is a recruitment issue, we will analyze the enrollment data and discuss possible causes in order to determine a solution.

Little evidence exists regarding clinically important sex/gender and/or race/ethnicity differences which could be associated with benefits or risks of varying tooth brushing frequency in mechanically ventilated adults. In addressing the exploratory study aim (to investigate patient factors that influence tooth brushing frequency benefit and risk in critically ill adults), we will include sex, ethnicity, and race as possible patient-level predictors in our analyses of risk and benefit.

Inclusion of Children. The target adult ICUs include patients who are 18 years or older. Children less than 18 years of age are not admitted to these ICUs and will not be recruited. Childhood dentition is significantly different from that of adults. The number of subjects ages 1-17 required for study enrollment to obtain adequate power to account for differences in dentition would be prohibitive and an adequate sample of children under 18 could not be obtained during the proposed study period.

### C. RESEARCH MATERIAL

Data will be obtained from the patient's medical record, from assessment of the subject's mouth, and from biologic fluids (gingival crevicular fluid, GCF, collected on filter paper). On study admission, the following data will be collected: demographic data (age, gender, smoking status, reason for admission), severity of illness data (APACHE information), and a count of decayed, missing and filled teeth (DMFT). The following data will be collected every day through the first seven days of mechanical ventilation, or until extubated if extubation occurs within the first seven days: digital photos of all teeth (for use in UM-OHI dental plaque assessment), a sample of GCF collected on Periopaper (for GCF IL-1 $\beta$  assay), Systemic Inflammatory Response Syndrome criteria from the medical record, positive epidemiologic surveillance reports for enrolled subjects for VAE (including VAP), bacteremia, and sepsis from the TGH Epidemiology Department records. For subjects who are extubated during the first 7 days of mechanical ventilation, the same data collected during the study intervention period will also be collected after extubation on days 1,3,5 after extubation. Data regarding length of intubation, length of ICU stay and length of hospital stay will also be calculated from the medical record.

### D. RECRUITMENT PLAN

All patients admitted to the adult Intensive Care Units at TGH who are intubated will be assessed for possible inclusion in the study. If a patient meets study criteria (age 18 or older, within 36 hours of initial intubation, have at least one tooth, and they or their legally authorized representative able to provide informed consent in English or Spanish) and has no exclusions (anticipation by the clinical provider of imminent patient death, or medical contraindication to tooth brushing), the potential subject will be approached for a discussion about willingness to participate. If the subject is unable to provide consent due to sedation or inability to communicate, the legally authorized representative (LAR) will be approached, the study will be reviewed and permission for the subject to participate will be obtained from the LAR; in these cases, we will attempt to obtain assent of the subject as well, and will make additional attempts to consent the subject directly as their condition improves. In our experience, potential subjects who are critically ill, especially during the first 36 hours of intubation, are always sedated to some degree, and their ability to communicate effectively is compromised by endotracheal intubation; for these reasons, permission for the subject's participation has generally been obtained from the LAR. However, there may be rare occurrences when potential subjects are adequately oriented and lucid to be able to provide informed consent. Therefore, we will use a 2 step procedure (developed by Fan et al) to determine the patient's ability to provide informed consent. Step 1 is objective evaluation with the Richmond Agitation-Sedation Scale (RASS) and the Confusion Assessment Method for Intensive Care Unit (CAM-ICU). Patients who score -1, 0, +1 on the RASS indicating drowsy, alert, or restless respectively and are not delirious (CAM-ICU = No) will move to Step 2. Step 2 is assessment for competency using the MacArthur Competence Assessment Tool for Clinical Research: MacCAT-CR. This is the most widely used tool, and is the only tool that evaluates all four capacity domains (understanding, appreciation, reasoning, expression of a choice). Evaluation of Step 1 requires approximately 2-3 minutes, Step 2 requires approximately 15 minutes. Fan et al. found in consent evaluations of 150 ICU patients that 89% were sedated/delirious, and unable to provide consent; our experience in previous research is similar. Therefore, we expect that few potential subjects will move to Step 2. The LAR will then be contacted for those who fail Step 1 or Step 2. Subject's willingness to continue participation will be assessed on an ongoing basis throughout the project. We will follow the USF and TGH IRB Written Policies and Procedures, as well as the Florida regulations regarding appropriate use and definition of the LAR.

### E. POTENTIAL RISKS

We anticipate minimal additional physical and psychological risks associated with this study. The intervention, tooth brushing, is routinely provided to critically ill patients by bedside nurses as part of clinical care. Organisms dislodged from dental plaque during tooth brushing might increase risk of HAIs if they are aspirated (contributing to VAP) or translocate into the bloodstream (contributing to bacteremia and sepsis); evaluation of safety is a specific aim of the proposed project. Data collection methods (including GCF collection by Periopaper and digital photographs of teeth) are non-invasive. Subjects may elect not to participate and may withdraw from the study at any time without affecting the care they receive.

### F. RISK REDUCTION

The intervention will be interspersed with the care team's activities, and at no time will the study personnel delay or interfere with clinical care; if the needs and activities of providers are such that the study personnel are unable to access

the subject to provide interventions, the subject will be withdrawn from the study. At all times we will place the subject's need for medical treatment, and avoidance with interference with treatment, foremost.

In order to reduce risks to privacy of individuals or confidentiality of data, we will not include personally identifiable data in the database files. All computers and data files will be password protected, and data will be stored on the University server, with access only to study personnel, under the direct supervision of [name]. Because these subjects are receiving clinical care in the hospital, the attending clinical medical providers will be promptly informed of any adverse effects to the subjects; if an adverse event occurs, necessary interventions will be determined and delivered by the clinical providers.

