## IX. RESEARCH DESIGN AND METHODS

### Design

We will use a prospective, randomized, experimental design to accomplish the specific aims. Subjects (n=345) will be randomly assigned within 36 hours of intubation to one of three intervention groups which differ in frequency of tooth brushing (once, twice, or three times daily). The intervention, a standardized tooth brushing protocol developed and tested in the previous project, will be delivered by study personnel. Subjects will continue to receive scheduled interventions for the first 7 days of intubation, or until extubated if extubation occurs within 7 days; for subjects extubated within the intervention period, data collection will continue on days 1, 3, and 5 post-extubation. Dental plaque assessment, GCF for IL-1 $\beta$  determination, and data regarding HAIs and clinical status (for example, severity of illness) will be collected daily by study personnel who are blinded to group assignment.

All subjects will receive standard clinical care for mechanically ventilated patients, as per clinical guidelines and clinical agency guidelines. Standard clinical care includes all components of the IHI ventilator care bundle, including daily CHX. All subjects will receive oral comfort care by clinical providers at the provider's discretion. We will monitor reported compliance with the ventilator care bundle, and record characteristics and frequency of oral comfort care provided in order to assure that groups do not differ in usual clinical care.

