**Serious Outcomes: SIRS, VAE and HAIs.** We will obtain data from the subject's medical record to evaluate SIRS criteria (heart rate > 90, respiratory rate > 20 or PaCO2 < 32 mm Hg, WBC > 12,000 mm^3 or < 4000 mm^3 or > 10% bands, temperature > 38 °C or < 36 °C) prior to the first tooth brushing intervention and daily thereafter while tooth brushing interventions continue. We will also monitor the results of any blood cultures obtained for clinical purposes from our subjects during the study period in order to identify clinical bacteremia. TGH has a robust surveillance program for

identification of bacteremia, VAC (including VAP), and sepsis. We will obtain HAI surveillance data regarding all study subjects from the Hospital Epidemiologist, as well as collecting data from each subject's medical record regarding diagnoses of these conditions by the clinical providers. We will also calculate length of intubation and length of stay for all subjects.

Sample Description and Patient Factors. Data will be collected from the medical record on additional factors in order to provide a comprehensive description of the study sample and conduct an exploration of the influence of individual-level factors on tooth brushing benefit and risk. Demographic data will be collected on study admission, and include age, gender, race, ethnicity, and smoking status. Preexisting global oral health will be measured by DMFT (Decayed, Missing, and Filled Tooth) Index assessed at study admission. The DMFT is a classic instrument which is widely used in dental practice and research. The score is calculated by visually inspecting each tooth and adding the number of decayed teeth, absent teeth, and filled teeth. Scores can range from a score of 0 (all teeth present and without caries) to a score of 32 (every tooth evidencing dental disease through loss, active dental caries, or repaired dental disease). The summative score will be used in examination of the exploratory aim. Severity of illness will be documented on admission to the study using the Acute Physiology, Age, and Chronic Health Evaluation (APACHE III). The APACHE III total score may range from 0 to 299 and consists of the following sub-scores: vital sign/lab, pH/pCO2, neurological, age, and chronic health. Scoring is done using the worst values for the first ICU day.

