Specific Aim 1 is to evaluate the clinical equivalence (non-inferiority) of three tooth brushing frequencies on oral health (dental plaque and mucosal inflammation) in critically ill adults receiving mechanical ventilation. To evaluate non-inferiority, we will use data from subjects who have at least 2 days duration of mechanical ventilation and at least 2 days of their randomly assigned tooth brushing regimen. Recognizing variable length of hospital stay and intubation, we will determine as the primary outcome the maximum difference in dental plaque since baseline assessment at the time of intubation. Whereas we would expect balanced distribution of the specific post-admission day in which this maximum difference is achieved between the 3 treatment arms (e.g. day 4, day 5, etc.), timing of the assessment will be included as a covariate along with baseline dental plaque score. Analysis of covariance (ANCOVA) will be used to compare adjusted dental plaque scores between the 1 and 3 times daily tooth brushing regimens. The test for non-inferiority of the single daily brushing regimen will be based on the 95% confidence interval for the adjusted difference between the 2 groups. For this analysis, we define non-inferiority as a modest between-group effect size of 0.50 or less (i.e. modest to low treatment effect associated with tooth brushing 3 times daily). Thus, if the upper limit of the confidence interval for the effect size is <0.50, then the single daily brushing regimen will be considered non-inferior to the 3 times daily tooth brushing regimen. If the non-inferiority test is not supported, a secondary test of the 1 versus 2 times daily brushing regimens will be conducted. Using this strategy, a direct test of non-inferiority of 2 versus 3 times daily is not required (see Table 2).

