Specific Aim 2 is to quantify and compare the safety of three tooth brushing frequencies on serious adverse outcomes, including ventilator associated complications and clinically relevant healthcare-associated infections. For aim #2, a composite HAI endpoint will be constructed consisting of VAP, bacteremia, and sepsis. Since HAIs are anticipated to be rare events across the 3 tooth brushing regimens, no formal between-group statistical testing will be conducted. Instead, 95% confidence intervals will be calculated for the proportion of subjects with HAI in each treatment arm. In addition, using person days of observation (i.e. days since intubation), we will calculate incidence rates (IR) of HAI by treatment arm and then calculate the number needed to harm (NNH) using the single daily brushing regimen as the

reference group and the formulas:  $NNH_{21} = (1 / (IR_2 - IR_1))$  and  $NNH_{31} = (1 / (IR_3 - IR_1))$  where  $IR_n$  = observed incidence rate in each treatment arm. In the event that the formal test of non-inferiority fails for the single daily brushing regimen, we will define clinically-relevant “compromised” safety as an NNH of 100 per less. This would be interpreted as 100 individuals or less being treated with the multiple daily tooth brushing to develop an HAI that otherwise would not have occurred with the single daily brushing regimen.

Clinical recommendations defined *a priori* and developed from the analyses conducted for aims 1 and 2 will be developed as defined in Table 2.

Table 2. Application of study findings to tooth brushing frequency recommendations

Comparison Groups a	Non-Inferiority	NNH	Recommendation	Rationale
1 versus 3	Supported	N/A	1 time/day	1 time/day non-inferior and safe
1 versus 3	Not supported	$\geq 100$	3 times/day	1 time/day inferior, 3 times/day safe
1 versus 3	Not supported	$< 50$	1 time/day	1 time/day inferior, but 3 times/day safety concern
1 versus 3	Not supported	50 to 100	See 1 vs. 2	1 time/day inferior, but 3 times/day safety concern
1 versus 2 b	Supported	N/A	1 time/day	1 time/day non-inferior and safe
1 versus 2 b	Not supported	$\geq 100$	2 times/day	1 time/day inferior, 2 times/day safe
1 versus 2 b	Not supported	$< 100$	1 times/day	1 time/day inferior, but 2 times/day safety concern

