aTimes per day of tooth brushing. bConducted if the 1 versus 3 test of non-inferiority is not supported and  $NNH_{31}$  is between 50 to 100. NNH: number needed to harm.

Specific Aim 3, to investigate patient factors that influence tooth brushing frequency benefit and risk in critically ill adults, is considered exploratory. Repeated measures linear mixed models will be fit treating dental plaque and mucosal inflammation as separate outcome variables (transformed if required), random group assignment as a 3-level ordinal predictor variable, and a range of possible patient-level predictors. Initially, bivariate correlations for potential continuous predictors and analysis of variance (ANOVA) for potential categorical predictors will be conducted to identify potential patient factors independently associated with dental plaque and mucosal inflammation. Interaction terms between tooth brushing frequency (scored 1, 2, or 3) and individual patient factors will be constructed to assess potential effect modification. The mixed models will be fit using the normal distribution, identity link, and specifying an autoregressive correlation structure. For assessment of safety, and assuming a sufficient number of HAs for model conversion, generalized estimating equations will be fit in the same manner as the linear mixed models while specifying the binomial distribution, log link, and an autoregressive correlation structure. Through these analyses, we aim to gain insight as to specific patient factors (e.g. presenting oral health) that may modify the clinical effectiveness and safety profile associated with frequency of tooth brushing.

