#### **G. ADDITIONAL SAFEGUARDS IF ANY PARTICIPANTS WILL BE VULNERABLE**

The trained Project Director or GRAs will review the potential subject's medical record, and if there are no exclusions, the subject will be invited to enroll. The subject and the subject's LAR will be provided with an oral explanation of the nature of the study and study information, in writing. The information will include all elements required for informed consent, and will include all pertinent contact information as well as information about withdrawal from the study. If at any time the subject or LAR does not wish to continue to participate in the study, no additional interactions with the subject will take place, no follow-up data will be collected and that subject's data forms will be destroyed. The study staff will work closely with the staff of the ICUs, the nurse managers and medical directors to ensure that all eligible patients have an equal opportunity for inclusion.

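### Withdrawal for blocked access and the 2-day regimen rule act after randomisation and can depend on arm; the plan has no supporting wider-set analysis for Aim 1 and no stated HAI follow-up for those withdrawn (minor)

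*Combined protocol and SAP*

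**What the plan says.** Section XVI.F (Risk Reduction) puts clinical care first. If provider activity prevents staff from reaching "the subject to provide interventions, the subject will be withdrawn from the study". This is removal from the study, not only from brushing. The section does not say whether one session, one day or a longer period triggers it, or whether outcome collection goes on.

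Section XI, Specific Aim 1, restricts the non-inferiority comparison to subjects with "at least 2 days duration of mechanical ventilation and at least 2 days of their randomly assigned tooth brushing regimen". It does not define a day of regimen, for example whether every scheduled session must have been given. The groups "differ in frequency of tooth brushing (once, twice, or three times daily", so a complete day needs one, two or three accesses.

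Section XI states no wider-set analysis and no missing-data method for the Aim 1 test. The Aim 3 paragraph says "Repeated measures linear mixed models will be fit treating dental plaque and mucosal inflammation as separate outcome variables", with no 2-day limit. Those models are exploratory, do not test non-inferiority and do not feed Table 2.

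For safety, the Serious Outcomes paragraph promises: "We will obtain HAI surveillance data regarding all study subjects from the Hospital Epidemiologist". Specific Aim 2 reports per-arm HAI proportions and incidence rates "using person days of observation (i.e. days since intubation", and the NNH comes from those rates. No analysis set is named. Section XVI.G says that when the subject or representative no longer wishes to take part, "no follow-up data will be collected and that subject's data forms will be destroyed". It does not mention withdrawal for blocked access.

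**The concern.** Randomisation makes the arms comparable, and a condition applied afterwards can undo that if it removes different kinds or numbers of subjects by arm. Here the number of accesses needed is the treatment itself. If one blocked session is enough for withdrawal, the three-times arm has three times the exposure to that event. If every session of a day must fail, the once-daily arm is the more exposed. The wording allows either.

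Table 2 turns the Aim 1 result and the NNH into a practice recommendation. Without a planned wider set, a reader could not confirm that the selection was harmless for the test that drives the table. For HAI the loss would also be avoidable, because those data come from records and surveillance and need no bedside access.

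**Working it through.** **The plan's own figures.** Margin 0.50 SD, one-sided alpha 0.10, power 95%: n = 2 × [(1.2816 + 1.6449)/0.50]² = 68.5, so 69 per group. Then 3 × 69 = 207 and 207/0.60 = 345, which is 115 randomised per arm. For HAI, a proportion of 0.05 with n = 69 gives an exact 95% interval of 0.012 to 0.131, matching the stated 0.01 to 0.13. That precision uses the Aim 1 evaluable size; with 115 it would be about 0.02 to 0.11.

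**Assumptions, since the documents give no rates.** q = share of sessions blocked, 1% or 3%, independent between sessions; k = 1, 2 or 3 sessions per day; 2 qualifying days. Subjects lost differ from those retained by δ = 0.25 to 0.50 SD in plaque change, after the planned covariate adjustment.

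**Aim 1: share lost over 2 days, by reading of the withdrawal rule**

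| Reading | Formula | q | 1× | 2× | 3× |
|---|---|---|---|---|---|
| (a) first blocked session | 1 − (1 − q)^(2k) | 1% | 2.0% | 3.9% | 5.9% |
| (a) | same | 3% | 5.9% | 11.5% | 16.7% |
| (b) access fails for whole days | 1 − (1 − q)², q per day | any | equal | equal | equal |
| (c) every session of a day blocked | 1 − (1 − q^k)² | 3% | 5.9% | 0.2% | under 0.01% |

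The retained mean differs from the full-arm mean by (share lost) × δ, so the shift in the 3× v 1× contrast is (gap in share lost) × δ.

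- (a) at 1%: gap 0.0386, shift 0.010 to 0.019 SD.
- (a) at 3%: gap 0.1079, shift 0.027 to 0.054 SD.
- (b): zero.
- (c) at 3%: gap −0.059, shift 0.015 to 0.030 SD with the arms reversed.

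Under (a) this is 2% to 11% of the margin. The sign depends on whether those lost would have had more or less plaque.

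**Effect on the decision.** The rule uses a 95% interval, so at a true difference of exactly 0.50 false non-inferiority is 2.5%. With SE = √(2/69) = 0.170, it becomes 1 − Φ(1.96 ∓ shift/SE). Under (a) that is 2.9% to 5.0% if the shift favours non-inferiority, and 2.2% down to 1.1% if it goes the other way.

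**A higher rate.** At 5% blocked, (a) loses 9.8% / 18.5% / 26.5%, and the shift is 0.04 to 0.08 SD. At 10% it would remove 46.9% of the three-times arm in two days, more than the plan's 40% allowance for all causes of unusable data.

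**HAI, only if follow-up ends at withdrawal.** Take reading (a), 7 planned days, a constant hazard and a true 5% in each arm. Expected observed days = Σ (1 − q)^(kj), j = 0 to 6.

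- q = 1%: 6.79 (1×) v 6.41 (3×). Observed proportions, days × 0.05/7, are 4.9% v 4.6%.
- q = 3%: 6.40 v 5.41. Observed proportions are 4.6% v 3.9%.
- Person-day rate at q = 3%: 0.0457/6.40 and 0.0386/5.41 are both 0.0071 per day. The rate difference behind the NNH stays at zero, provided that person-days stop when event collection stops and loss is unrelated to HAI risk.

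**Dilution in a wider set.** Suppose a share w of it has half the arm contrast. The effect is 0.50 − 0.25w and n = 69/(1 − w) per arm.

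| w | Effect | SE | False non-inferiority at a true 0.50 |
|---|---|---|---|
| 10% | 0.475 | 0.162 | 3.6% |
| 20% | 0.450 | 0.152 | 5.1% |
| 30% | 0.425 | 0.142 | 7.6% |
| 40% | 0.400 | 0.132 | 11.5% |

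The 40% row corresponds to all 115 per arm and is an upper value, because some subjects will have no usable score.

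**The case against.** The withdrawal sentence speaks of interventions in the plural, after saying that brushing is fitted around care. That reads more naturally as a continuing lack of access than as one missed session, and under the whole-day reading the Aim 1 shift is zero. This stands as a reason to expect a small effect. It does not settle the rule, because no trigger is given.

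Requiring exposure in a non-inferiority comparison is defensible, since barely treated subjects pull the arms together. This also stands: the dilution figures can exceed the bias being checked, so the 2-day set should stay primary. Early-extubated subjects whose only scores follow a return to self-care should not enter a wider set.

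A reader might infer that the HAI gap distorts the NNH and so Table 2. The documents do not support that: the NNH uses person-day rates, which allow for unequal observation, and nothing shows that blocked access is related to HAI risk. Nor do they support the inference that data on access withdrawals are destroyed, because Section XVI.G covers only withdrawal by the subject or representative. The promise of surveillance data on all study subjects may well be meant to include access withdrawals. It does not say so.

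**Conclusion.** The point holds as a minor one. Two stated rules act after randomisation and can remove different shares of each arm; no supporting analysis is planned for the Aim 1 test; and HAI follow-up after an access withdrawal is not stated.

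The likely Aim 1 effect is small: zero if whole days are blocked, and up to about 0.05 SD at an assumed 3% of sessions blocked with a 0.50 SD difference in those lost. A reader might infer a bias towards or against once-daily brushing. The documents support neither, because the direction depends on the trigger and on who is lost. The per-arm HAI proportions would be under-counted unequally if collection stopped at withdrawal (4.6% v 3.9% at worst in the 1% to 3% range). The rates and NNH change only if loss is related to HAI risk. All blocking rates and differences are assumptions, and the stated sample size is not in question here.

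**What to change.** 1. **Section XVI.F.** Record blocked access as missed brushing, not as study withdrawal. Continue HAI, SIRS and length-of-stay collection from records and surveillance, subject to consent. This changes study status and data only; the priority of clinical care is untouched.
2. **Section XI, Aim 2.** Analyse HAI proportions and person-day rates in all randomised subjects by assigned arm, except data removed under Section XVI.G. Report those removals by arm.
3. **Section XI, Aim 1.** Define a day of regimen. Keep the 2-day set as the primary set that drives Table 2. Add one sensitivity analysis by assigned arm in all subjects with a baseline and at least one post-baseline plaque score taken while intubated, using no post-extubation scores. Report exclusions by arm and reason.
4. **Rule for disagreement.** State in advance that the wider set is supportive only. It cannot rescue a failed test in the 2-day set, and a disagreement is reported as a limit on the conclusion.

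The cost is protocol wording and one extra analysis; the record-based follow-up needs no bedside access. The consent pages were not available for this review, so permission to keep using records after blocked access must be confirmed. The downside is the dilution shown above (about 3.6% to 11.5% false non-inferiority if 10% to 40% of the wider set has half the contrast), which is why that set should not replace the primary one.
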